1.3 Schedule of Activities

1.3.1 Scheduled Visits for Base Study

Visit Number	1	2	3	4	5	6	7	8	9	10	11	12	13	Notes
	Day 1													
Scheduled Day/Month		2	6	7	12	18	24	30	36	42	48	54	60 (Final Visit)	
Visit Window ¹		± 3 Weeks	± 4 Weeks	3 to 7 Weeks Postdose 3				ź	± 1 mo	onth				To calculate visit windows, assume 1 month=30 days and 1 week=7 days
Administrative Procedures														
Obtain Informed Consent	X													
Obtain Informed Consent for Future Biomedical Research	X													Participation in future biomedical research is optional and consent must be obtained before collection of blood (DNA) samples.
Review Inclusion/Exclusion Criteria	X													
Assign Participant Identification Card	X													
Collect Lifetime Medical History (includes substance usage)	X													Substances: Alcohol, tobacco
Update Medical History (new conditions not already recorded as medical history or AEs)		X	X	X	X	X	X	X	X	X	X	X	X	
Collect Lifetime Sexual History	X													
Collect Sexual Activity		X	X	X	X	X	X	X	X	X	X	X	X	Sexual activity will not be collected after initial database lock and unblinding.
Review Prior/Concomitant Medication and Non-study Vaccination Review	X	X	X	X	X	X	X	X	X	X	X	X	X	See Section 6.5 for prerequisites for medications and non-study vaccines

Visit Number	1	2	3	4	5	6	7	8	9	10	11	12	13	Notes
Scheduled Day/Month		2	6	7	12	18	24	30	36	42	48	54	60 (Final Visit)	
Visit Window ¹		± 3 Weeks	± 4 Weeks	3 to 7 Weeks Postdose 3		± 1 month					To calculate visit windows, assume 1 month=30 days and 1 week=7 days			
Clinical and Laboratory Proc	edures													
Measure Oral Temperature	X	X	X											Prior to each vaccination. Participants who have a fever (defined as an oral temperature of ≥37.5°C) within the 24-hour period prior to vaccination must be rescheduled.
Record Height and Weight	X													Prior to vaccination.
Physical Examination (optional, per investigator's discretion; perform if needed to assess inclusion/exclusion criteria)	X													
Anogenital Physical Examination	X													Prior to vaccination
Genitourinary examination for external genital lesions	X			X	X	X	X	X	X	X	X	X	X	Prior to vaccination on Day 1 Examination will not be required after initial database lock and unblinding.
Penile/glans penis file and wetted swab for HPV PCR	X			X	X	X	X	X	X	X	X	X	X	Prior to vaccination on Day 1 Sample should not be collected after initial database lock and unblinding.

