Participants will be followed for solicited injection-site AEs Days 1 through Days 5 following each vaccination, and any other injection-site AEs and systemic AEs Days 1 through Days 15 following each vaccination. Any SAEs regardless of causality will be recorded from the time of randomization through 6 months postdose 3. Vaccine-related SAEs and deaths will be collected throughout the study. New medical conditions (defined as incident medical conditions occurring outside of Days 1 to Days 15 period following each vaccination and not considered SAEs) will be recorded for all participants at each study visit throughout the study.

The primary analysis is case driven. The database will be locked, and the primary analysis will be conducted after at least 17 primary efficacy endpoint cases and at least 17 secondary efficacy endpoint cases have been observed in the base study. There is no interim analysis planned in this study. These efficacy results as well as immunogenicity and safety results based on data in the initial database lock for the primary analysis will be reported as the primary CSR. All participants will be unblinded after the primary efficacy analysis database lock. Once a participant is unblinded, no further efficacy samples will be collected from the participant.

Once at least 17 primary endpoint cases and at least 17 secondary efficacy endpoint cases are accrued, each participant will proceed to the Final Visit promptly without completing any other scheduled visits in order to complete the base study (as shown in Section 1.3, and Section 8.12.1.4). Additional database locks will be executed, including a second database lock after the completion of the final efficacy sample assessment for the purpose of the final efficacy analysis and a final database lock of the base study after the last participant's Final Visit in the base study for the final immunogenicity and safety analysis, respectively. Cumulative data collected from the initiation of the study will be summarized separately and a report will be written after each database lock. The base study will end after the last participant completes their Final Visit in the base study.

Extension Study

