8.1.4 Medical History

A medical history will be obtained by the investigator. At Visit 1 (Day 1) in the base study, the participant's lifetime medical history of genitourinary or HPV-related diagnoses will be collected. Other medical history for the year prior to Visit 1 will be collected.

After the Day 1 visit, any new medical history that has not been previously documented (ie, incident medical conditions occurring outside of Days 1 to Days 15 period postvaccination and not considered SAEs) will be collected throughout the base study. In the extension study, any new medical history will not be collected.

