8.5 Adverse Events, Serious Adverse Events, and Other Reportable Safety Events

The definitions of an AE or SAE, as well as the method of recording, evaluating, and assessing causality of AE and SAE and the procedures for completing and transmitting AE, SAE, and other reportable safety event reports can be found in Appendix 3.

Adverse events, SAEs, and other reportable safety events will be reported by the participant (or, when appropriate, by a caregiver, surrogate, or the participant's legally authorized representative).

The investigator and any designees are responsible for detecting, documenting, and reporting events that meet the definition of an AE or SAE as well as other reportable safety events. Investigators need to document if an SAE was associated with a medication error, misuse, or abuse.

Investigators remain responsible for following up AEs, SAEs, and other reportable safety events for outcome according to Section 8.5.3. The investigator, who is a qualified physician, will assess events that meet the definition of an AE or SAE as well as other reportable safety events with respect to seriousness, intensity and causality.

8.5.1 Time Period and Frequency for Collecting AE, SAE, and Other Reportable Safety Event Information

All AEs, SAEs, and other reportable safety events that occur after the participant provides documented informed consent, but before randomization, must be reported by the investigator if they cause the participant to be excluded from the study, or are the result of a protocol-specified intervention, including, but not limited to washout or discontinuation of usual therapy, diet, placebo, or a procedure.

Base Study:

From the time of randomization through 14 days following the first vaccination(s) and from the time of any subsequent vaccination(s) through 14 days thereafter, all AEs must be reported by the investigator. All SAEs and other reportable safety events that occur from the time of randomization through 6 months following the last vaccination must be reported by the investigator, regardless of whether the events are considered to be vaccine-related by the investigator.

Extension Study:

SAEs and death will be collected from the first dose of vaccination until 1 month after the last dose.

V503-064-03 FINAL PROTOCOL 24-SEP-2024

Base Study and Extension Study:

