Additionally, any SAE brought to the attention of an investigator at any time outside the period specified in the previous paragraph also must be reported immediately to the Sponsor if the event is either:

• A death that occurs before the participant completing the study, but outside the period specified in the previous paragraph.

OR

• An SAE that is considered by an investigator, who is a qualified physician, to be vaccine related.

Investigators are not obligated to actively seek AEs or SAEs or other reportable safety events in former study participants. However, if the investigator learns of any SAE, including a death, at any time after a participant has been discharged from the study, and the investigator considers the event to be reasonably related to the study intervention or study participation, the investigator must promptly notify the Sponsor.

All initial and follow-up AEs, SAEs, and other reportable safety events will be recorded and reported to the Sponsor or designee within the time frames as indicated in Table 3.

Table 3 Reporting Periods and Time Frames for Adverse Events and Other Reportable Safety Events

Type of Event NSAE	Reporting Time Period: Consent to Randomization/ Allocation Report if: - due to protocol- specified intervention - causes exclusion - participant is receiving placebo run-in or other run-	Reporting Time Period: Randomization/ Allocation through Protocol- specified Follow- up Period Report all	Reporting Time Period: After the Protocol- specified Follow- up Period Not required	Time Frame to Report Event and Follow-up Information to Sponsor: Per data entry guidelines
SAE	in treatment Report if: - due to protocol- specified intervention - causes exclusion - participant is receiving placebo run-in or other run- in treatment	Report all	Report if: - drug/vaccine related any death until participant completion of study (Follow ongoing to outcome)	Within 24 hours of learning of event
Cancer	Report if: - due to intervention - causes exclusion	Report all	Not required	Within 5 calendar days of learning of event (unless serious)
Overdose NSAE=nonserious a	Report if: - receiving placebo run-in or other run- in medication dverse event; SAE=serious a	Report all	Not required	Within 5 calendar days of learning of event

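### Sections 4.1 and 8.1.4 exclude SAEs from new medical conditions even after all-cause SAE reporting has ended; the Schedule of Activities does not, so it is unclear where a late, serious, unrelated condition is recorded

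*Combined protocol and SAP*

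**What the plan says.** **SAE stream.** Section 4.1: "Any SAEs regardless of causality will be recorded from the time of randomization through 6 months postdose 3". Section 8.5.1 ties the end of the window to a different dose: "All SAEs and other reportable safety events that occur from the time of randomization through 6 months following the last vaccination must be reported". For the time after the window, Section 4.1 says "Vaccine-related SAEs and deaths will be collected throughout the study", and the SAE row of Table 3 limits reporting to "drug/vaccine related any death until participant completion of study". The cancer row of Table 3 requires no report after the window.

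**New-condition stream.** Section 4.1 records new medical conditions at each visit throughout the study and defines them as "incident medical conditions occurring outside of Days 1 to Days 15 period following each vaccination and not considered SAEs". Section 8.1.4 collects them throughout the base study and defines them as "incident medical conditions occurring outside of Days 1 to Days 15 period postvaccination and not considered SAEs".

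**Schedule of Activities.** The row in Section 1.3.1, marked at every visit from Month 2 to Month 60, applies a different test: "Update Medical History (new conditions not already recorded as medical history or AEs". It excludes what has already been recorded and says nothing about seriousness.

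**Analysis.** Table 7 gives between-arm intervals for all-cause SAEs only for Days 1 through 15 after vaccination, and for vaccine-related SAEs at any time. New medical conditions are Tier 3, that is, counts and percentages by group.

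**The concern.** Two collection streams that are meant to complement each other should leave no gap between them. Here one is closed to serious events for the whole base study, and the other closes to unrelated, non-fatal serious events 6 months after the last dose. From that point a site that follows Sections 4.1 and 8.1.4 records a minor new illness and has no defined place for a hospitalisation with new disease that the investigator calls unrelated. A site that follows the Schedule of Activities records both.

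The long-term record by arm could therefore keep the mild conditions and lose serious ones. What is lost would depend on an individual causality judgement and on which section a site reads. New medical conditions is the only row of Table 7 that describes late, unrelated illness, so the omission would not be made good elsewhere in the planned tables.

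**Working it through.** **1. The plan's own SAE figure.** Section 9.9.3 gives a 93% chance of at least one SAE among 525 vaccinees at an incidence of 0.5%: 1 − 0.995^525 = 0.928. With no events, the one-sided 95% bound is 1 − 0.05^(1/525) = 0.57%, which agrees with the stated <0.6%. Both figures reproduce. They are proportions of participants with no time window attached, so they say nothing about late capture.

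**2. Trace one event.** Take a hospitalisation at Month 24 for a newly diagnosed chronic disease, non-fatal and judged unrelated.
- Is it an SAE? Inpatient hospitalisation meets Section 10.3.3. Section 10.3.2 counts new conditions diagnosed after study intervention as AEs, and Section 8.5.1 itself speaks of SAEs outside the reporting period.
- Is it reportable as an SAE? No. It is past the window, not a death and not vaccine-related (Section 8.5.1, Table 3).
- Is it a new medical condition under Sections 4.1 and 8.1.4? No, because it is considered an SAE.
- Is it due under the Schedule of Activities row? Yes, because it is not already recorded.
- A non-serious illness at the same visit is recorded under all three texts.

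**3. When the gap opens.** Dose 3 is due at Month 6 ± 4 weeks (28/30 = 0.93 month). Adding 6 months gives 6 − 0.93 + 6 = 11.1 to 6 + 0.93 + 6 = 12.9, so about Month 12. Under Section 8.5.1 it opens near Month 6 after one dose only and near Month 8 after two. Section 4.1 counts from dose 3 and so gives no end date for a participant who never had it.

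**4. Longest gap.** 60 − 12 = 48 months, and 48/60 = 80% of maximum follow-up.

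**5. Person-time.** Inputs from Sections 9.9 and 9.9.1: 1050 participants, 14 months of enrolment (taken as uniform), 5% attrition per year, 56 months from first consent. Let λ = −ln 0.95 = 0.0513 per year. Follow-up f runs from 42 to 56 months (3.50 to 4.67 years), mean 49 months (4.08 years).
- After Month 12: 1050 × (0.95 − mean of 0.95^f)/λ = 1050 × (0.950 − 0.811)/0.0513, about 2,840 (2,842 by numerical averaging over enrolment).
- All follow-up, same formula with 1 in place of 0.95: about 3,866. Share after Month 12: 2,842/3,866 = 74%.
- If everyone were followed to Month 60, with the same attrition: 3,607 of 4,631, or 78%.

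**6. Events.** A count would be 2,842 multiplied by a yearly rate of non-fatal, unrelated serious conditions. The documents give no such rate, so the calculation stops at person-time.

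**The case against.** The strongest reply is that the event does have a place. The Schedule of Activities row would take it at every visit to Month 60, and Section 8 makes adherence to that schedule essential and required. No text gives Sections 4.1 and 8.1.4 precedence over it. This stands, and it rules out the stronger reading that such an event is recorded nowhere. It does not remove the contradiction. Section 4.1 sends the reader to Section 8 for the detail of each procedure, and Section 8.12.1.4 refers the Final Visit medical-history update to Section 8.1.4, which is the restrictive wording.

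A second reply is that an AE must be temporally associated with study intervention (Section 10.3.2) and that a non-AE cannot be an SAE (Section 10.3.3). A late unrelated illness would then not be an SAE and would pass as a new medical condition. Section 8.4.4 points the same way, since it has the investigator decide whether a new condition is to be reported as an SAE. This is weak. Section 8.5.1 refers to SAEs outside the window, Section 10.3.2 counts later-diagnosed conditions as AEs, and Section 8.4.4 concerns vaccination report card review, which ends at Month 7.

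Third, other routes exist. Deaths and vaccine-related SAEs are collected throughout. External genital cancers reach the Pathology Panel while efficacy sampling continues. Abnormal results from optional STI testing go to new medical history without regard to seriousness (Section 8.1.13). All-cause SAEs are collected again in the extension. These narrow the gap and stand as far as they go. The extension cannot restore a comparison between arms, because it is open label and vaccine recipients who completed the series are not eligible (Section 5.1.2).

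Finally, the limited all-cause SAE window is itself a design choice, and the data entry guidelines, which are not in the documents, may already settle the matter. Both points are fair. The concern here is not the length of the window but that the protocol's own definitions disagree about what is collected after it.

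**Conclusion.** The concern holds as an inconsistency with a practical consequence. As Sections 4.1, 8.1.4 and 8.5.1 define the two streams, a serious, non-fatal condition judged unrelated and arising more than 6 months after the last dose falls outside both. The Schedule of Activities row would include it. Capture may therefore differ between sites.

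Up to 48 of 60 months per participant are exposed, and about 2,840 person-years (74% of follow-up) on the planning assumptions in step 5. Forty-eight months is a maximum, since follow-up ends when the case counts are reached.

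Two stronger inferences are not supported. A reader might put a figure on the serious events that would go unrecorded. That needs a yearly rate the documents do not give, and it would also assume that every site ignores the Schedule of Activities. A reader might also infer that a planned safety test is compromised. It is not: the between-arm intervals for all-cause SAEs cover Days 1 through 15 only, the new-conditions row is descriptive, and the efficacy hypotheses are untouched. What is at risk is the completeness of that Tier 3 summary.

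**What to change.** In Sections 4.1 and 8.1.4, change the exclusion from conditions considered SAEs to conditions reported as SAEs. Both then agree with the Schedule of Activities row. A serious incident condition outside the SAE reporting window is recorded as a new medical condition and counted by arm in the existing Tier 3 row. A seriousness flag on that form would let these be shown separately, but it is optional.

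In the same edit, reconcile the end of the all-cause SAE window between Section 4.1 (counted from dose 3) and Section 8.5.1 (counted from the last vaccination), so that it is defined for participants who did not receive dose 3.

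The cost is a few words in each section and slight additional data entry. No visit is added and expedited SAE reporting does not change. Because Section 8.12.1.4 keeps the medical-history update at the Final Visit even after unblinding, the clarification could still recover conditions in participants who have not yet had that visit.

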4.2 Scientific Rationale for Study Design

This study is designed to evaluate the 9vHPV vaccine efficacy against HPV 6/11/16/18related anogenital persistent infection and HPV 31/33/45/52/58-related anogenital persistent infection, respectively. The qHPV vaccine efficacy findings associated with the 4 HPV types in V501-020 will be extrapolated to the 9vHPV vaccine, via the demonstration of the efficacy similarities against HPV type 6, 11, 16 or 18-related anogenital persistent infection in V501-122 with qHPV vaccine. Considering the comparison between this study data and previous study data (V501-122), 16 to 26 years old in both HM and MSM are selected as this study population in a manner consistent with Protocol V501-122. The enrollment of approximately 10% MSM participant will be targeted in this study. Please note "10%" is a target number considering the challenging nature of MSM enrollment in Japan from operational aspect. In addition, participants will be enrolled regardless of the history of circumcision. This study targeted young males with a maximum of 5 female (HM) and/or male (MSM) sexual partners in order to minimize the proportion of enrolled subjects who were HPV positive at baseline. In addition, in order to obtain a cohort with a reasonable risk of becoming infected after the vaccination series was completed, virgins were excluded from the study, with the exception of MSMs who identified themselves as a male who has had sex with males or must have engaged in oral sex with another male within the last year.

4.2.1 Rationale for Endpoints

4.2.1.1 Efficacy Endpoints

Efficacy endpoints based on precancerous lesions (high-grade intraepithelial dysplasia) were used in clinical studies with the qHPV and the 9vHPV vaccines to demonstrate protection from cervical, vulvar, vaginal, and anal cancers and precancers caused by vaccine HPV types. Results from efficacy clinical trials of the qHPV vaccine have shown that participants with HPV 16/18-related persistent infection were at a greater risk of HPV 16/18-related highgrade cervical dysplasia. In contrast, participants without persistent infection were unlikely to develop HPV 16/18-related high-grade cervical disease [Radley, D., et al 2016]. Similar results were observed in the pivotal study of the 9vHPV vaccine (Protocol V503-001) for the endpoints of HPV 31/33/45/52/58-related persistent infection and HPV 31/33/45/52/58related high-grade disease (MSD unpublished data). This suggests that HPV 16/18/31/33/45/52/58-related persistent infection is appropriate as a surrogate endpoint for HPV 16/18/31/33/45/52/58-related high-grade cervical disease. Although HPV infection has been primarily studied in the context of cervical cancer, the results are considered applicable to other squamous epithelial cancers (including cancers of vulva, vagina, anal canal, oral cavity, pharynx, and larynx), that are susceptible to infection by high-risk HPV types [Gillison, M.L., et al 2012].

The primary efficacy endpoint is the incidence of HPV 6-, 11-, 16- or 18-related anogenital persistent infection. This endpoint was chosen based on the finding from two previous

studies of qHPV vaccine. One is the Japanese Phase 3 study that demonstrated the efficacy of qHPV vaccine against HPV 6-, 11-, 16- or 18-related anogenital persistent infection in Japanese males (Protocol V501-122). The other is the previous global Phase 3 study (V501-020) that qHPV vaccine showed prophylactic efficacy against HPV 6-, 11-, 16- or 18-related AIN and genital warts as well as HPV 6-, 11-, 16- or 18-related persistent infection in 16- to 26-year-old males, suggesting HPV related anogenital persistent infection is a predictor of HPV related anogenital diseases in males. For the purpose of bridging qHPV vaccine efficacy against HPV 6-, 11-, 16- or 18-related AIN and genital warts to 16- to 26-year-old Japanese males who received the 9vHPV vaccine, the incidence of HPV 6-, 11-, 16- or 18-related anogenital persistent infection was selected as the primary efficacy endpoint in this study as well as in V501-122.

As the secondary endpoint, the incidence of the other 5 types of HPV (31-, 33-, 45-, 52- or 58)-related anogenital persistent infection will also be assessed similarity with the 9vHPV vaccine efficacy finding associated with the 5 HPV types in V503-001 that was global Phase 3 study in 16- to 26-year-old females including Japanese females.

